5.2.1.2 Dose Interval Modification for Non-Hepatic Drug-Related Adverse Events

Adverse events associated with pembrolizumab exposure may represent an immunologic etiology. These immune-related AEs (irAEs) may occur shortly after the first dose or several months after the last dose of pembrolizumab treatment, and may affect more than 1 body system simultaneously. Therefore, early recognition and initiation of treatment is critical to reduce complications. Based on existing clinical trial data, most irAEs were reversible and could be managed with interruptions of pembrolizumab, administration of corticosteroids, and/or other supportive care. For suspected irAEs, ensure adequate evaluation to confirm etiology or exclude other causes. Additional procedures or tests such as bronchoscopy, endoscopy, or skin biopsy may be included as part of the evaluation. Based on the severity of irAEs, withhold or permanently discontinue pembrolizumab and administer corticosteroids. Dose modification and toxicity management guidelines for non-hepatic irAEs associated with pembrolizumab are provided in [Table 3](#).

Table 3 Dose Modification and Toxicity Management Guidelines for Non-hepatic Immune-related AEs Associated with Pembrolizumab

Dose modification, diagnosis, and management guidance for hepatic events of clinical interest is provided in Section 5.2.1.3.

| General instructions: | | | | | |
|------------------------------|---|--------------------------------------|--|--|--|
| Immune-related AEs | Toxicity grade or conditions (CTCAEv4.0) | Action taken to pembrolizumab | irAE management with corticosteroid and/or other therapies | Monitor and follow-up | |
| Pneumonitis | Grade 2 | Withhold | 
 Administer corticosteroids (initial dose of 1-2 mg/kg prednisone or equivalent), followed by taper | 
 Monitor subjects for signs and symptoms of pneumonitis Evaluate subjects with suspected pneumonitis with radiographic imaging and initiate corticosteroid treatment Add prophylactic antibiotics for opportunistic infections | |
| | Grade 3 or 4, or recurrent Grade 2 | Permanently discontinue | | | |

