6.0 TRIAL FLOW CHART

6.1 Initial Treatment with Study Drug

| Trial Period: | Screening Phase | Treatment Cycles (3-Week Cycles) | | | | | | | | End of Treatment | Post-Treatment | | |
|--|-----------------|----------------------------------|----|----|----|----|----|----|----|-------------------|------------------------|----------------------------|---------------------------------|
| Treatment Cycle/Title: | Screening | 1 | 2 | 3 | 4 | 5 | 6 | 7 | ≥8 | Discon | Safety Follow-up | Follow-up Visits | Survival Follow-up ^a |
| Scheduling Window (Days) ^b | -28 to -1 | | ±3 | ±3 | ±3 | ±3 | ±3 | ±3 | ±3 | At Time of Discon | 30 Days Post Last Dose | Every 12 Weeks Post Discon | Approx. Every 12 Weeks |
| Administrative Procedures | | | | | | | | | | | | | |
| Informed consent | X | | | | | | | | | | | | |
| Informed consent for future biomedical research (optional) | X | | | | | | | | | | | | |
| Inclusion/exclusion criteria | X | | | | | | | | | | | | |
| Subject identification card | X | | | | | | | | | | | | |
| Demographics and medical history (including smoking and alcohol use) | X | | | | | | | | | | | | |
| Prior and concomitant medication review | X | X | X | X | X | X | X | X | X | | | | |
| Post-study anticancer therapy status | | | | | | | | | | | X | X | X |
| Survival status ^a | | <-----> | | | | | | | | | | | X |
| Clinical Procedures/Assessments | | | | | | | | | | | | | |
| Review adverse events ^c | X | X | X | X | X | X | X | X | X | | X | X | |
| Full physical examination | X | | | | | | | | | | X | X | |

| Trial Period: | Screening Phase | Treatment Cycles (3-Week Cycles) | | | | | | | | End of Treatment | Post-Treatment | | |
|---|------------------|----------------------------------|----|----|----|----|----|----|----------------|-------------------|------------------------|----------------------------|---------------------------------|
| | | 1 | 2 | 3 | 4 | 5 | 6 | 7 | ≥8 | | Safety Follow-up | Follow-up Visits | Survival Follow-up ^a |
| Treatment Cycle/Title: | Screening | | | | | | | | | At Time of Discon | 30 Days Post Last Dose | Every 12 Weeks Post Discon | Approx. Every 12 Weeks |
| Scheduling Window (Days) ^b | -28 to -1 | | ±3 | ±3 | ±3 | ±3 | ±3 | ±3 | ±3 | ±3 | ±7 | ±7 | ±7 |
| Directed physical examination | | X | X | X | X | X | X | X | X | | | | |
| Child-Pugh Score ^d | X ^e | | | | | | | | | | | | |
| Height, weight, and vital signs (T, P, RR, BP) ^f | X | X | X | X | X | X | X | X | X | | | | |

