| c. SAEs will be followed through 90 days following cessation of treatment, or 30 days following cessation of treatment if the subject initiates new anticancer therapy, whichever is earlier. All protocol specific hepatic ECIs will be collected throughout the study as listed in Section 7.2.3.2. If any of the hepatic ECI criteria are met, collect the Child-Pugh score until the hepatic ECIs resolve. | | | | | | | | | | | | | | | | | | | | |
| d. If any of the hepatic ECI criteria are met, document the Child Pugh score with each visit until the hepatic ECIs resolve. | | | | | | | | | | | | | | | | | | | | |
| e. ECOG Performance Status, Child-Pugh Score, and laboratory tests for screening and determining eligibility are to be performed within 7 days prior to the first dose of trial treatment except hepatitis and thyroid tests, which may be performed within 28 days. | | | | | | | | | | | | | | | | | | | | |
| f. Height will be measured at Visit 1 only. | | | | | | | | | | | | | | | | | | | | |
| g. Upper endoscopy to be performed at any time within 12 months before the first dose of study drug. | | | | | | | | | | | | | | | | | | | | |
| h. See Section 4.2.4.3 for details regarding administration of Patient Reported Outcomes (PROs). All PROs are to be performed at Cycle 1, Cycle 2, Cycle 3, Cycle 4, | | | | | | | | | | | | | | | | | | | | |

| Trial Period: | Screening Phase | Treatment Cycles (3-Week Cycles) | | | | | | | | End of Treatment | Post-Treatment | | | |
|---------------------------------------|-----------------|--|----|----|----|----|----|----|----|-------------------|------------------------|----------------------------|---------------------------------|--|
| | | 1 | 2 | 3 | 4 | 5 | 6 | 7 | ≥8 | | Safety Follow-up | Follow-up Visits | Survival Follow-up ^a | |
| Treatment Cycle/Title: | Screening | | | | | | | | | At Time of Discon | 30 Days Post Last Dose | Every 12 Weeks Post Discon | Approx. Every 12 Weeks | |
| Scheduling Window (Days) ^b | -28 to -1 | | ±3 | ±3 | ±3 | ±3 | ±3 | ±3 | ±3 | ±3 | ±7 | ±7 | ±7 | |

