7.1.6.3.2 Follow-up Visits

Subjects who discontinue trial treatment for reasons other than disease progression will move into the Follow-up Phase and should be assessed Q12W by radiologic imaging to monitor disease status. Every effort should be made to collect information regarding disease status until the start of a new anti-cancer therapy, disease progression, death, or the end of the study.

Information regarding post-study anti-cancer treatment will be collected if new treatment is initiated.

Subjects who are eligible to receive retreatment according to the criteria in Section 7.1.4.1.4 will move from the Follow-up Phase to the Second Course Phase when they experience disease progression.

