7.1.6.3.3 Survival Follow-up

Subjects, who experience disease progression (by site assessment) or start a new anti-cancer therapy, will move into the Survival Follow-Up Phase. Subjects should be contacted (by telephone or visit) approximately every 12 weeks to assess for survival status until death, withdrawal of consent, or the end of the study, whichever occurs first. Post-study anti-cancer therapy will be collected during survival follow-up.

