All adverse events that occur after the consent form is signed but before treatment allocation/randomization must be reported by the investigator if they cause the subject to be excluded from the trial, or are the result of a protocol-specified intervention, including but not limited to washout or discontinuation of usual therapy, diet, placebo treatment or a procedure. From the time of treatment allocation/randomization through 30 days following cessation of treatment, all adverse events must be reported by the investigator. Such events will be recorded at each examination on the Adverse Event case report forms/worksheets. The reporting timeframe for adverse events meeting any serious criteria is described in section 7.2.3.1. The investigator will make every attempt to follow all subjects with non-serious adverse events for outcome.

Electronic reporting procedures can be found in the Electronic Data Capture (EDC) data entry guidelines. Paper reporting procedures can be found in the Investigator Trial File Binder (or equivalent).

7.2.1 Definition of an Overdose for This Protocol and Reporting of Overdose to the Sponsor

In this trial, an overdose is any dose higher than ≥ 1000 mg (5 times the protocol defined dose) of pembrolizumab. No specific information is available on the treatment of over dose of pembrolizumab. In the event of overdose, study treatment should be discontinued and the subject should be observed closely for signs of toxicity. Appropriate supportive treatment should be provided if clinically indicated.

If an adverse event(s) is associated with (“results from”) the overdose of Sponsor's product or vaccine, the adverse event(s) is reported as a serious adverse event, even if no other seriousness criteria are met.

If a dose of Sponsor's product or vaccine meeting the protocol definition of overdose is taken without any associated clinical symptoms or abnormal laboratory results, the overdose is reported as a non-serious Event of Clinical Interest (ECI), using the terminology “accidental or intentional overdose without adverse effect.”

All reports of overdose with and without an adverse event must be reported by the investigator within 24 hours to the Sponsor either by electronic media or paper. Electronic reporting procedures can be found in the EDC data entry guidelines. Paper reporting procedures can be found in the Investigator Trial File Binder (or equivalent).

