7.2.3 Immediate Reporting of Adverse Events to the Sponsor

7.2.3.1 Serious Adverse Events

A serious adverse event is any adverse event occurring at any dose or during any use of Sponsor's product that:

- Results in death;
- Is life threatening;
- Results in persistent or significant disability/incapacity;
- Results in or prolongs an existing inpatient hospitalization;
- Is a congenital anomaly/birth defect;
- Is an other important medical event.

Note: In addition to the above criteria, adverse events meeting either of the below criteria, although not serious per ICH definition, are reportable to the Sponsor in the same timeframe as SAEs to meet certain local requirements. Therefore, these events are considered serious by the Sponsor for collection purposes.

- Is a new cancer (that is not a condition of the study);
- Is associated with an overdose.

Refer to [Table 7](#) for additional details regarding each of the above criteria.

For the time period beginning when the consent form is signed until treatment allocation/randomization, any serious adverse event, or follow up to a serious adverse event, including death due to any cause, other than progression of the cancer under study (reference Section 7.2.3.3 for additional details), that occurs to any subject must be reported within 24 hours to the Sponsor if it causes the subject to be excluded from the trial, or is the result of a protocol-specified intervention, including but not limited to washout or discontinuation of usual therapy, diet, placebo treatment or a procedure.

For the time period beginning at treatment allocation/randomization through 90 days following cessation of treatment, or 30 days following cessation of treatment if the subject initiates new anticancer therapy, whichever is earlier, any serious adverse event, or follow up to a serious adverse event, including death due to any cause, other than progression of the cancer under study (reference Section 7.2.3.3 for additional details) whether or not related to the Sponsor's product, must be reported within 24 hours to the Sponsor either by electronic media or paper. Electronic reporting procedures can be found in the EDC data entry

guidelines. Paper reporting procedures can be found in the Investigator Trial File Binder (or equivalent).

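### Subjects who stop for progression and start no new therapy have a 90-day SAE window but no scheduled adverse-event review after day 30

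*Combined protocol and SAP*

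**What the plan says.** **Reporting duty.** All adverse events are reported for 30 days after treatment (Section 7.2): "From the time of treatment allocation/randomization through 30 days following cessation of treatment, all adverse events must be reported by the investigator". The period for SAEs is longer. Footnote c to flow chart 6.1 states: "SAEs will be followed through 90 days following cessation of treatment, or 30 days following cessation of treatment if the subject initiates new anticancer therapy". The shorter of the two periods applies. Section 7.2.3.1 sets the same window, regardless of relatedness, with reporting to the sponsor within 24 hours.

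**Contacts after treatment.** Section 7.1.6.3.1 makes one Safety Follow-up Visit mandatory, at about 30 days after the last dose or before new therapy. The paths then divide:

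- Section 7.1.6.3.2: "Subjects who discontinue trial treatment for reasons other than disease progression will move into the Follow-up Phase", with 12-weekly visits.
- Section 7.1.6.3.3: subjects with site-assessed progression, or who start new therapy, enter Survival Follow-up. There, "Subjects should be contacted (by telephone or visit) approximately every 12 weeks to assess for survival status". Post-study anticancer therapy is also recorded. Nothing else is listed.

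**Flow charts.** In both 6.1 and 6.2 the row "Review adverse events" is marked at Safety Follow-up and at Follow-up Visits, and is empty under Survival Follow-up.

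**The concern.** The duty to report SAEs runs to day 90, but the schedule gives one group no occasion after day 30 on which anyone must ask about them. That group is subjects who stop for progression and start no new anticancer therapy. A survival call is made to them in any case, and it carries no adverse-event question.

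The protocol gives a reason to want late events found. Section 5.2.1.2 says immune-related events "may occur shortly after the first dose or several months after the last dose of pembrolizumab treatment". Liver deterioration after progression is also easily put down to the cancer, and Section 7.2.3.3 exempts progression itself from SAE reporting.

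What is at stake is the completeness of non-fatal SAE counts in days 31-90, and whether ascertainment is the same for subjects who stop for different reasons. Any serious AE and any serious drug-related AE are both Tier 2 safety endpoints (Section 8.6.2, Table 12). The issue is how events are found within the agreed window, not how long the window should be.

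**Working it through.** The plan states no figure to reproduce here. The check sets the duty beside the schedule and then asks what can be said about size.

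**1. Duty against schedule, for a subject with no new therapy by day 90**

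| | Stops for progression | Stops for another reason |
|---|---|---|
| SAE window (7.2.3.1, footnote c) | to day 90 | to day 90 |
| Safety visit with AE review (7.1.6.3.1) | about day 30 | about day 30 |
| Next contact | Survival Follow-up, about 12-weekly | Follow-up Visit, 12-weekly after discontinuation |
| AE review marked there (6.1, 6.2) | no | yes |

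Section 7.1.2.1 ties adverse-event assessment to the flow chart, so the blank cell matters.

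**2. Length of the gap**

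90 − 30 = 60 days; 60/90 = 67% of the window.

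**3. Where the first survival contact falls**

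The flow charts give about 12 weeks (84 days) with a ±7-day window. Section 7.1.6.3.3 gives no starting point.

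- Counted from discontinuation: 84 − 7 = day 77 to 84 + 7 = day 91.
- Counted from the day-30 visit: 30 + 84 = about day 114.

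On the first count the call may come before the window closes. A call on day 77 leaves days 78-90, or 13 days, still to run. On the second count it comes well after the window has closed.

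**4. Who is affected**

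Under Section 7.2.3.1 new therapy cuts the window to 30 days. Section 7.1.6.3.1 is worded differently and runs it until new therapy starts. On either reading, the full 60-day gap applies only to progressors who start no new therapy by day 90:

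affected = 408 × p × q

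Here p is the share stopping for site-assessed progression and q is the share of those starting no new therapy by day 90. The documents give neither.

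The nearest figures are 331 projected PFS events and 183 projected deaths among 408 subjects at Month 22 (Section 8.7.1). The share with progression as first PFS event then lies between two extremes:

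- every projected death is a first event: (331 − 183)/408 = 148/408 = 36%;
- no death comes first: 331/408 = 81%.

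This only roughly brackets p. PFS uses central review, and a PFS event is not the same as stopping treatment for progression. With q unknown, no count of affected subjects follows.

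**The case against.** The strongest reply is that other sections already require these events to be captured.

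- Section 7.2.3.1 obliges the investigator to report every SAE in the window, and related SAEs at any time if they come to attention.
- Section 7.1.6.3.1 follows adverse events above Grade 1 to resolution or new therapy.
- Section 5.8.1 requires data on clinical events after discontinuation to be collected through the last scheduled follow-up.
- Section 7.1.2.1 has adverse events recorded during follow-up, and assessed more often than the chart if clinically indicated.
- Footnote c has hepatic events of clinical interest collected throughout the study.
- Deaths surface at the survival contact itself.

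Much of this stands. It narrows the gap to new, non-fatal SAEs, but does not close it. A duty to report does not schedule a question. Following known events does not find new ones. Section 5.8.1 points back to the same flow chart and post-treatment visits. The hepatic provision is not a firm backstop either: Section 7.2.3.2 ends that reporting duty at 30 days, and no laboratory tests are marked under Survival Follow-up. The data-entry guidelines and trial file binder are not among the documents. They may contain a prompt, but the protocol cites them for how to report, not when to ask.

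The contrast with non-progressors should also not be overdrawn. Their first Follow-up Visit falls at about days 77-91, so they too have no review between day 30 and about day 77. The difference is one retrospective question, not 60 days of active surveillance.

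**Conclusion.** The gap is real and narrow. For subjects who stop for site-assessed progression and start no new anticancer therapy, days 31-90 of the SAE window have no scheduled adverse-event review. New non-fatal SAEs then may be under-ascertained. This is a cheap improvement to safety data collection; it does not touch the efficacy analyses.

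A reader might infer three stronger things, and the documents do not support them:

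- **That most of the trial is affected.** The 81% figure counts PFS events, deaths included, on central review. It says nothing about who starts new therapy by day 90.
- **That SAEs will be missed.** Reporting duties still apply, and no number of missed events can be estimated.
- **That the arm comparison is biased.** Section 8.6.1.2 expects control subjects to stop treatment earlier, but each subject's window starts at that subject's own last treatment, so earlier stopping alone changes nothing. A difference in ascertainment would need the arms to differ in the share stopping for progression without new therapy. The design PFS hazard ratio of 0.60 makes that possible, but nothing shows its size or direction. Section 8.6.2 also treats the Tier 2 intervals as descriptive.

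The verdict assumes that the blank flow-chart cells are intended, and that no operational document supplies the missing question.

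**What to change.** 1. In flow charts 6.1 and 6.2, mark an SAE review at the first Survival Follow-up contact, with a footnote limiting it to subjects who have started no new anticancer therapy.
2. State that this first contact is counted from the last dose and takes place at or just after day 90, for example day 90 with a window of +7 days, so that one call looks back over the whole SAE window.
3. Add the SAE question to Section 7.1.6.3.3, beside survival status and later therapy.

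The SAE window, the later survival contacts and the treatment rules stay as they are. The cost is one question in a contact that already takes place and may be by telephone, a few more SAE reports to process, and a fixed date for the first survival call. The change will not find immune-related events that start after day 90; those still depend on the existing duty to report related SAEs that come to the investigator's attention.

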7.1.6.4 Survival Status

To ensure current and complete survival data are available at the time of database locks, updated survival data may be requested during the course of the trial by the Sponsor. For example, updated survival status may be requested prior to but not limited to an external Data Monitoring Committee eDMC review, interim, and/or final analysis. Upon Sponsor notification, all subjects who do not/will not have a scheduled study visit or study contact during the Sponsor-defined time period will be contacted for their survival status (excluding subjects who have a previously recorded death event in the collection tool).

7.2 Assessing and Recording Adverse Events

An adverse event is defined as any untoward medical occurrence in a patient or clinical investigation subject administered a pharmaceutical product and which does not necessarily have to have a causal relationship with this treatment. An adverse event can therefore be any unfavourable and unintended sign (including an abnormal laboratory finding, for example), symptom, or disease temporally associated with the use of a medicinal product or protocol-specified procedure, whether or not considered related to the medicinal product or protocol-specified procedure. Any worsening (i.e., any clinically significant adverse change in frequency and/or intensity) of a preexisting condition that is temporally associated with the use of the Sponsor's product, is also an adverse event.

Changes resulting from normal growth and development that do not vary significantly in frequency or severity from expected levels are not to be considered adverse events. Examples of this may include, but are not limited to, teething, typical crying in infants and children and onset of menses or menopause occurring at a physiologically appropriate time.

Sponsor's product includes any pharmaceutical product, biological product, device, diagnostic agent or protocol-specified procedure, whether investigational (including placebo or active comparator medication) or marketed, manufactured by, licensed by, provided by or distributed by the Sponsor for human use.

Adverse events may occur during clinical trials, or as prescribed in clinical practice, from overdose (whether accidental or intentional), from abuse and from withdrawal.

Progression of the cancer under study is not considered an adverse event.

All adverse events that occur after the consent form is signed but before treatment allocation/randomization must be reported by the investigator if they cause the subject to be excluded from the trial, or are the result of a protocol-specified intervention, including but not limited to washout or discontinuation of usual therapy, diet, placebo treatment or a procedure. From the time of treatment allocation/randomization through 30 days following cessation of treatment, all adverse events must be reported by the investigator. Such events will be recorded at each examination on the Adverse Event case report forms/worksheets. The reporting timeframe for adverse events meeting any serious criteria is described in section 7.2.3.1. The investigator will make every attempt to follow all subjects with non-serious adverse events for outcome.

Electronic reporting procedures can be found in the Electronic Data Capture (EDC) data entry guidelines. Paper reporting procedures can be found in the Investigator Trial File Binder (or equivalent).

7.2.1 Definition of an Overdose for This Protocol and Reporting of Overdose to the Sponsor

In this trial, an overdose is any dose higher than ≥ 1000 mg (5 times the protocol defined dose) of pembrolizumab. No specific information is available on the treatment of over dose of pembrolizumab. In the event of overdose, study treatment should be discontinued and the subject should be observed closely for signs of toxicity. Appropriate supportive treatment should be provided if clinically indicated.

If an adverse event(s) is associated with (“results from”) the overdose of Sponsor's product or vaccine, the adverse event(s) is reported as a serious adverse event, even if no other seriousness criteria are met.

If a dose of Sponsor's product or vaccine meeting the protocol definition of overdose is taken without any associated clinical symptoms or abnormal laboratory results, the overdose is reported as a non-serious Event of Clinical Interest (ECI), using the terminology “accidental or intentional overdose without adverse effect.”

All reports of overdose with and without an adverse event must be reported by the investigator within 24 hours to the Sponsor either by electronic media or paper. Electronic reporting procedures can be found in the EDC data entry guidelines. Paper reporting procedures can be found in the Investigator Trial File Binder (or equivalent).

